10.3.2.1 Primary Endpoint(s)

The primary endpoint is the incidence and severity of all treatment-related adverse events.

10.3.2.2 Secondary Endpoint(s)

The secondary endpoints include:

1) Incidence and severity of all treatment-related select adverse events which are as follows:

- Pulmonary toxicity
- Gastrointestinal toxicity (diarrhea or colitis)
- Endocrinopathies
- Hepatotoxicity (including asymptomatic LFT elevations)
- Renal toxicity
- Skin toxicity
- Neurological toxicity
- Hypersensitivity/infusion reactions

2) Incidence of serious treatment-related adverse events

3) Incidence and severity of adverse events that lead to discontinuation.

All safety data will be summarized and listed for all treated participants. All on-study AEs, SAEs, treatment-related AEs, treatment-related SAEs and select AEs will be summarized using worst grade per NCI CTCAE v4.0 by system organ class and Medical Dictionary for Regulatory Affairs (MedDRA) preferred term. On-study laboratory abnormalities including hematology, chemistry, liver function, thyroid function, and renal function will be summarized using worst grade per NCI CTCAE v4.0 criteria.

[REDACTED]

12 APPENDICES

[REDACTED]

[REDACTED]	[REDACTED]	[REDACTED]	[REDACTED]
[REDACTED]	[REDACTED]	[REDACTED]	[REDACTED]
[REDACTED]	[REDACTED]	[REDACTED]	[REDACTED]
[REDACTED]	[REDACTED]	[REDACTED]	[REDACTED]
[REDACTED]	[REDACTED]	[REDACTED]	[REDACTED]
[REDACTED]	[REDACTED]	[REDACTED]	[REDACTED]
[REDACTED]	[REDACTED]	[REDACTED]	[REDACTED]
[REDACTED]	[REDACTED]	[REDACTED]	[REDACTED]
[REDACTED]	[REDACTED]	[REDACTED]	[REDACTED]
[REDACTED]	[REDACTED]	[REDACTED]	[REDACTED]
[REDACTED]	[REDACTED]	[REDACTED]	[REDACTED]
[REDACTED]	[REDACTED]	[REDACTED]	[REDACTED]
[REDACTED]	[REDACTED]	[REDACTED]	[REDACTED]
[REDACTED]	[REDACTED]	[REDACTED]	[REDACTED]
[REDACTED]	[REDACTED]	[REDACTED]	[REDACTED]

APPENDIX 2 ABBREVIATIONS AND TRADEMARKS

Term	Definition
AE	adverse event
ALK	Alkaline phosphatase
ALT	alanine aminotransferase
ANC	absolute neutrophil count
AST	Aspartate aminotransferase
β-HCG	beta-Human Chorionic Gonadotrophin
BA/BE	bioavailability/bioequivalence
%BE	percent biliary excretion
BMS	Bristol-Myers Squibb
BP	blood pressure
BTLA	B and T lymphocyte attenuator
BUN	blood urea nitrogen
Ca ⁺⁺	calcium
CBC	complete blood count
CD28	cluster of differentiation 28
C _{expected-tau}	expected concentration in a dosing interval
CFR	Code of Federal Regulations
CI	confidence interval
Cl ⁻	chloride
CL _{cr}	creatinine clearance
cm	centimeter
C _{max} , C _{MAX}	maximum observed concentration
C _{min} , C _{MIN}	minimum observed concentration
CNS	Central nervous system
CRF	Case Report Form, paper or electronic
CTLA-4	cytotoxic T lymphocyte antigen-4
C _{trough}	Trough observed plasma concentration
CV	coefficient of variation
CYP	cytochrome p-450

Term	Definition
D/C	discontinue
dL	deciliter
ECG	electrocardiogram
EC50	half maximal effective concentration
ECOG	Eastern Cooperative Oncology Group
eCRF	Electronic Case Report Form
EDC	Electronic Data Capture
eg	exempli gratia (for example)
EGFR	estimated glomerular filtration rate.
F	bioavailability
FDA	Food and Drug Administration
FSH	follicle stimulating hormone
g	gram
GCP	Good Clinical Practice
GGT	gamma-glutamyl transferase
h	hour
HBsAg	hepatitis B surface antigen
HBV	Hepatitis B virus
HCO ₃ ⁻	bicarbonate
HCV ab	hepatitis C virus antibody
HCV RNA	hepatitis C virus ribonucleic acid
HIV	Human Immunodeficiency Virus
HR	heart rate
HRT	hormone replacement therapy
ICD	International Classification of Diseases
ICH	International Conference on Harmonisation
IC50	half maximal inhibitory concentration
ie	id est (that is)
IEC	Independent Ethics Committee
IL	interleukin
IMP	investigational medicinal products

Term	Definition
IND	Investigational New Drug Exemption
IRB	Institutional Review Board
IU	International Unit
IV	intravenous
IVRS	interactive voice recognition system
kg	kilogram
L	liter
LDH	lactate dehydrogenase
mg	milligram
Mg ⁺⁺	magnesium
min	minute
mL	milliliter
mmHg	millimeters of mercury
MR	medical research
MS	mass spectrometry
MTD	maximum tolerated dose
µg	microgram
N	number of subjects or observations
Na ⁺	sodium
N/A	not applicable
ng	nanogram
NIMP	non-investigational medicinal products
NCI CTCAE	National Cancer Institute Common Terminology Criteria for AEs
NSCLC	non-small cell lung cancer
PD-1	programmed death-1
PS	Performance status
PT	prothrombin time
PTT	partial thromboplastin time
QC	quality control
RBC	red blood cell

Term	Definition
RCC	renal cell carcinoma
RR	respiration rate
SAE	serious adverse event
SD	standard deviation
SOP	Standard Operating Procedures
Subj	subject
t	temperature
T	time
T ₃	triiodothyronine
T ₄	thyroxine
TCR	T-cell receptor
TSH	thyroid stimulating hormone
UV	ultraviolet
W	washout
WBC	white blood cell
WHO	World Health Organization
WOCBP	women of childbearing potential

7.6.9	Vital Signs	26
█	█	
7.6.11	Pregnancy Testing	27
█	█	
█	█	

8	CONVENTIONS.....	27
9	CONTENT OF REPORTS.....	29
APPENDIX 1	SCHEDULE OF ACTIVITIES.....	30

LIST OF TABLES

Table 5-1 CA209887: Estimated Incidence Rates and 95 % CIs	13
Table 7.4-1: Administration of Study Therapy: Definition of Parameters.....	19
 	
Table 7.6-1: Select Adverse Events	32

LIST OF FIGURES

Figure 2-1: Study Design Schematic11

LIST OF ABBREVIATIONS

AE	adverse event(s)
AEOSI	other events of special interest
ALP	alkaline phosphatase
ALT	alanine aminotransferase
AST	Aspartate aminotransferase
BMI	body mass index
BMS	Bristol-Myers Squibb
BP	blood pressure
BUN	blood urea nitrogen
CBC	complete blood count
CI	confidence interval
CR	Complete response
CRF	Case Report Form, paper or electronic
CSR	Clinical Study Report
CTC	Common Terminology Criteria
CTCAE	Common Terminology Criteria for AEs
ECOG	Eastern Cooperative Oncology Group
HB	hemoglobin
HR	heart rate
IMAEs	Immune-mediated AEs
IMP	investigational medicinal products
IP	investigational product
IV	intravenous
IVRS	interactive voice recognition system
LDH	lactate dehydrogenase
LFT	liver function tests
LLN	lower limit of normal
MedDRA	Medical Dictionary for Regulatory Activities
NCI	National Cancer Institute
NSCLC	non-small cell lung cancer
NSQ	non-squamous
PD	Progressive disease
PR	Partial response
PS	Performance status
PT	Preferred Term
RCC	renal cell carcinoma
RR	respiratory rate
SAE	serious adverse event(s)

SAP	statistical analysis plan
SAS	Statistical Analysis System software
SD	Stable disease
SI	standard international unit
SOC	System Organ Class
SQ	squamous
TSH	thyroid stimulating hormone
ULN	upper limit of normal
US	United States
WHO	World Health Organization
WOCBP	women of childbearing potential

[REDACTED]

Research Hypothesis:

This study will describe the adverse reactions that occur during 6 months of treatment with nivolumab in patients with advanced NSCLC or RCC in India. No test of the statistical hypothesis is planned in this study.

Schedule of Analyses:

Data analyses will be conducted only on the safety data collected within the maximum of the 26 week study period, which will include safety collected during the follow-up of patients who discontinue treatment before 24 weeks.

Final analysis will be done once the study will be completed on the date on which safety data (primary endpoint) are collected for the last participant on study.

2 STUDY DESCRIPTION

2.1 Study Design

This is a Phase 4, open-label, single arm, multi-center, prospective safety study to be conducted in India with patients with either locally advanced or metastatic NSCLC (Stage IIIb/IV NSCLC) with squamous histology or non-squamous histology who have progressed during or after at least 1 prior chemotherapy (N= 70) or advanced RCC who have progressed during or after at least 1 prior therapy (N= 30). Potential patients will undergo screening evaluations to determine eligibility within 28 days prior to first dose. Patients who meet the protocol defined inclusion/exclusion criteria will be prospectively enrolled in a sequential manner. All enrolled patients will be treated with nivolumab administered intravenously over 60 minutes at 3 mg/kg every 2 weeks. Each 14 day dosing period will constitute a cycle. Treatment will continue as long as clinical benefit is observed for a maximum of 24 weeks or until treatment is no longer tolerated by the participant or withdrawal of consent. The treatment period for this study is 26 weeks, which corresponds to 24 weeks of treatment and 2 weeks of follow-up after the final on-study dose of nivolumab. Patients who are observed to continue to receive clinical benefit from nivolumab at 26 weeks will continue treatment via commercial supply (provided by BMS) as long as clinical benefit is observed or until treatment is no longer tolerated by the participant. Any participant who discontinues treatment with nivolumab before 24 weeks on study will be followed for 100 days after discontinuation of study drug or for a total of 26 weeks from first on-study treatment with nivolumab, whichever is earliest.

Safety will be evaluated throughout the treatment period and during the follow up of patients who discontinue treatment before 24 weeks by physical exams including vital signs, AE/SAE monitoring, laboratory evaluations and recording of concomitant medications.

All SAEs after 26 weeks of study duration for patients on commercial nivolumab supply will be reported to India Health Authority as part of spontaneous reporting.

The study design schematic is presented in Figure 2.1.

Figure 2-1: Study Design Schematic

- Participants who discontinue on-study treatment before 24 weeks will be followed for 100 days after last on-study dose of nivolumab or for 26 weeks after first on-study dose, whichever is earliest.
- Participants who continue to benefit clinically from nivolumab at 26 weeks will continue treatment via commercial supply (provided by BMS) as long as clinical benefit is observed or until treatment is no longer tolerated by the participant. All SAEs after 26 weeks of study duration for patients on commercial nivolumab supply will be reported to India Health Authority as part of spontaneous reporting.

Physical examinations, vital sign measurements, and clinical laboratory evaluations will be performed at selected times throughout the dosing interval and during follow-up for those patients who discontinue treatment before the end of the treatment period (24 weeks). Patients will be closely monitored for AEs throughout the study.

2.2 Treatment Assignment

After informed consent has been obtained and the subject's eligibility is established, the subject will be enrolled and a number will be assigned through an interactive voice response system (IVRS). All patients will receive treatment with nivolumab in an open-label fashion. Study treatment will be dispensed at the study visits as listed in Schedule of Activities ([Appendix 1](#)).

2.3 Blinding and Unblinding

This is an open-label study, blinding procedures are not applicable.

2.4 Protocol Amendments

Not applicable.

2.5 Data Monitoring and Other External Committees

Not applicable.

3 OBJECTIVES

3.1 Primary

- To assess the safety and tolerability of nivolumab for the treatment of locally advanced or metastatic NSCLC after prior chemotherapy or advanced RCC after prior therapy.

3.2 Secondary

- To estimate the incidence and severity of treatment-related select AEs in all treated patients.
- To estimate the incidence of all treatment-related SAEs
- To estimate the incidence of AEs that lead to discontinuation of treatment with nivolumab.

4 ENDPOINTS

4.1 Primary Endpoint

- Incidence and severity of all treatment-related AEs

4.2 Secondary Endpoints

- Incidence and severity of all treatment-related select AEs which are as follows
 - Pulmonary toxicity
 - Gastrointestinal toxicity (diarrhea or colitis)
 - Endocrinopathies
 - Hepatotoxicity (including asymptomatic liver function tests (LFT) elevations)
 - Renal toxicity
 - Skin toxicity
 - Neurological toxicity
 - Hypersensitivity/infusion reactions
- Incidence of all treatment-related SAEs
- Incidence of AEs that lead to discontinuation from treatment with nivolumab

5 SAMPLE SIZE AND POWER

The study is projected to enroll a minimum of 100 patients (70 NSCLC patients and 30 RCC patients). The total sample size for this study is based on logistical considerations. The sample size meets regulatory requirement for safety update submission.

In global clinical studies, treatment-related AEs of any grade occurred approximately 65% and of Grade 3-4 occurred approximately 10% in nivolumab users with NSCLC; treatment-related AEs

of any grade occurred approximately 80% and of grade 3-4 occurred approximately 20% in nivolumab users with RCC. Assuming these event rates, there is approximately 99% probability to observe at least 37 treatment-related AEs of any grade and approximately 84% probability to observe at least 5 treatment-related AEs of grade 3-4 in the 70 NSCLC patients; there is approximately 97% probability to observe at least 20 treatment-related AEs of any grade and approximately 88% probability to observe at least 4 treatment-related AEs of grade 3-4 in the 30 RCC patients.

Given the proposed sample size, the 95% confidence intervals for relevant AE rates are presented in Table 5-1.

Table 5-1 CA209887: Estimated Incidence Rates and 95 % CIs

Incidence Rate (%)	Sample Size	Lower 95% CI (%)	Upper 95% CI (%)
5	30	0.36	19.71
	70	1.22	13.01
	100	1.64	11.28
10	30	2.11	26.53
	70	4.12	19.52
	100	4.90	17.62
20	30	7.71	38.57
	70	11.39	31.27
	100	12.67	29.18
30	30	14.73	49.40
	70	19.62	42.13
	100	21.24	39.98
40	30	22.66	59.40
	70	28.47	52.41
	100	30.33	50.28
50	30	31.30	68.70
	70	37.80	62.20
	100	39.83	60.17
60	30	40.60	77.34

	70	47.59	71.53
	100	49.72	69.67
70	30	50.60	85.27
	70	57.87	80.38
	100	60.02	78.76

Exact confidence interval based on Clopper-Pearson method.

6 STUDY PERIODS, TREATMENT REGIMENS AND POPULATIONS FOR ANALYSES

6.1 Study Periods

6.1.1 *Baseline Period*

Baseline evaluations or events will be defined as evaluations or events that occur before the date and time of the first dose of study treatment. Evaluations on the same date and time of the first dose of study treatment will be considered as baseline evaluations.

In cases where the time (onset time of event or evaluation time and dosing time) is missing or not collected, the following definitions will apply:

- Pre-treatment AEs will be defined as AEs with an onset date prior to but not including the day of the first dose of study treatment
- Baseline evaluations (e.g., laboratory tests and vital signs) will be defined as evaluations with a date on or prior to the day of first dose of study treatment

If there are multiple valid assessments, the assessment that is closest to day (and time if collected) of the first dose of study treatment will be used as the baseline in the analyses. If multiple assessments are collected at the same date (and time if collected), the assessment with the latest database entry date (and time if collected) will be considered as baseline.

6.1.2 *Post Baseline Period*

- On-treatment AEs will be defined as AEs with an onset date and time on or after the date and time of the first dose of study treatment (or with an onset date on or after the day of first dose of study treatment if time is not collected or is missing). For subjects who are off study treatment, AEs will be included if event occurred within a safety window of 100 days after the last dose of study treatment or for a total of 26 weeks from first on-study treatment with nivolumab, whichever is earliest. No subtracting rule will be applied when an AE occurs both pre-treatment and post-treatment with the same preferred term and grade.

- On-treatment evaluations (laboratory tests and vital signs) will be defined as evaluations taken after the day (and time, if collected and not missing) of first dose of study treatment. For subjects who are off study treatment, evaluations should be within a safety window of 100 days after the last dose of study treatment or for a total of 26 weeks from first on-study treatment with nivolumab, whichever is earliest.
- Late emergent drug-related AEs will be defined as drug-related AEs with an onset date greater than 100 days after the last dose of study treatment in subjects who are off study treatment or for a total of 26 weeks from first on-study treatment with nivolumab, whichever is earliest.

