6.2 Treatment Regimens

Patients should receive nivolumab at a dose of 3 mg/kg as a 60-minute IV infusion, on Day 1 of each treatment cycle every 2 weeks for 24 weeks or until progression, unacceptable toxicity, withdrawal of consent, or the study ends, whichever occurs first. Patients should begin study treatment within 3 calendar days of enrollment.

Dosing calculations should be based on the body weight assessed at baseline. It is not necessary to re-calculate subsequent doses if the participant weight is within 10% of the weight used to calculate the previous dose. All doses should be rounded up or to the nearest milligram per institutional standard.

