7.3.6 Subsequent Systemic Cancer Therapy

A by-subject listing will be provided separately for subsequent systemic cancer therapy, radiotherapy for treatment of tumors and on-treatment/subsequent surgery for treatment of tumors.

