7.6.4 Adverse Events

Adverse events will be summarized by tumor type:

- Overall summary of any AEs by worst CTC grade (grade 1, 2, 3, 4, 5, unknown) presented by SOC/PT.
- Overall summary of drug-related AEs by worst CTC grade (any grade, grade 3-4, grade 5) presented by SOC/PT.

By-subject AE listing will be provided.

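### The on-treatment safety window ignores the start of a new anticancer therapy, so the all-cause, immune-mediated and laboratory tables can include toxicity of the next treatment

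*SAP*

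**What the plan says.** SAP 6.1.2 defines the on-treatment period for AEs by time since the last dose: "For subjects who are off study treatment, AEs will be included if event occurred within a safety window of 100 days after the last dose", with the limit "or for a total of 26 weeks from first on-study treatment with nivolumab, whichever is earliest". Laboratory tests and vital signs get the same treatment: "For subjects who are off study treatment, evaluations should be within a safety window of 100 days after the last dose of study treatment", with the same cap.

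Treatment can end well before 24 weeks. SAP 6.2 has dosing "every 2 weeks for 24 weeks or until progression, unacceptable toxicity, withdrawal of consent, or the study ends, whichever occurs first". Protocol 8.1 and 8.1.1 keep participants who stop early in follow-up.

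Subsequent treatment appears in one place, SAP 7.3.6: "A by-subject listing will be provided separately for subsequent systemic cancer therapy, radiotherapy for treatment of tumors", together with surgery. That section makes no link to the safety window.

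Several outputs carry no causality filter:

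- SAP 7.6.4 plans "Overall summary of any AEs by worst CTC grade (grade 1, 2, 3, 4, 5, unknown) presented by SOC/PT". SAP 7.6.2 (SAEs) and 7.6.5.1 (select AEs) have all-cause counterparts.
- SAP 7.6.7 counts immune-mediated AEs (IMAEs) whatever their cause.
- Protocol 10.3.2.2 adds "On-study laboratory abnormalities including hematology, chemistry, liver function, thyroid function, and renal function will be summarized using worst grade".

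The primary endpoint (SAP 4.1) and the secondary endpoints on select AEs and SAEs (SAP 4.2) are limited to treatment-related events. The remaining secondary endpoint is AEs leading to discontinuation of nivolumab.

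**The concern.** Participants have previously treated, advanced NSCLC or RCC, and progression is one reason to stop. Some may start another therapy while still inside the counted window. A cytopenia, transaminase rise, thyroid change, diarrhea or rash caused by that therapy would then be tabulated as an on-treatment finding. A laboratory grade carries no investigator attribution that could remove it.

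The study is single-arm and tests no hypothesis, so its tables are its result. A summary table gives no way to tell which events came after a switch. The distortion in the affected tables can only be upward, and it would fall mainly on participants who stopped early.

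**Working it through.** **The plan's own figures.** The only probability calculations are in SAP Section 5 (and Protocol 10.1). Exact binomial tails give 0.987 for at least 37 of 70 at 65%, 0.841 for at least 5 of 70 at 10%, 0.974 for at least 20 of 30 at 80%, and 0.877 for at least 4 of 30 at 20%. The plan states 99%, 84%, 97% and 88%. All 24 Clopper-Pearson intervals in SAP Table 5-1 also reproduce. These figures are sound, and this point does not depend on them.

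**Length of the window after the last dose.** Count days from the first dose as day 0, with doses on time every 14 days, so dose k falls on day d = 14(k − 1). Twenty-six weeks is 182 days.

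- Counted days after the last dose = min(100, 182 − d). The full 100 days applies when d is at most 82.
- Share of the whole window = those days / min(d + 100, 182).
- Days that could be spent on the next therapy = counted days − gap. The gap from last dose to next therapy is not in the documents; 14, 28 and 42 days are assumptions.

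| Last dose (day d) | Counted days after it | Share of window | Days on next therapy, gap 14 / 28 / 42 |
|---|---|---|---|
| Dose 4 (42) | 100 | 100/142 = 70% | 86 / 72 / 58 |
| Dose 6 (70) | 100 | 100/170 = 59% | 86 / 72 / 58 |
| Dose 8 (98) | 84 | 84/182 = 46% | 70 / 56 / 42 |
| Dose 9 (112) | 70 | 70/182 = 38% | 56 / 42 / 28 |
| Dose 11 (140) | 42 | 42/182 = 23% | 28 / 14 / 0 |

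The room for overlap is real and is largest in early stoppers.

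**Laboratory draws.** Time share is a poor guide here. During treatment a panel is drawn every cycle (Table 2-2). Follow-up has at most two scheduled panels, nominally 30 and 30 + 70 = 100 days after the last dose (Table 2-3). If dose 8 is the last, the second visit is nominally on day 98 + 100 = 198. Even with both 5-day tolerances used, it is on day 98 + 25 + 65 = 188, past the day-182 cap. From dose 8 on, only one scheduled follow-up panel can count.

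**Effect on a table.** One participant whose only qualifying event comes from the next therapy adds 1/70 = 1.4 points to the NSCLC column, 1/30 = 3.3 to RCC and 1/100 = 1.0 to the pooled column.

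An illustration beyond that needs assumptions. Let f be the share who start a new therapy inside the window (assumed 10-40%). Let q be the chance that it causes a Grade 3-4 event in someone otherwise free of one (assumed 10-50%). With true rate p, the observed rate is p + (1 − p) × f × q.

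- NSCLC, p = 10%: from 10 + 90 × 0.1 × 0.1 = 10.9% to 10 + 90 × 0.4 × 0.5 = 28.0%, or 0.6 to 12.6 extra participants of 70.
- RCC, p = 20%: from 20 + 80 × 0.1 × 0.1 = 20.8% to 20 + 80 × 0.4 × 0.5 = 36.0%, or 0.2 to 4.8 extra of 30.

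The p values are the plan's treatment-related rates, used as stand-ins because it gives no all-cause or laboratory rates. A range this wide shows that the documents do not fix the size.

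**Which outputs are exposed.**

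- All-cause AEs, SAEs and select AEs: exposed directly.
- IMAEs: most summaries require immune-modulating medication, which narrows the exposure. Endocrine IMAEs do not require it, and one summary drops every requirement beyond the preferred-term list. The criterion on alternate etiology applies only to studies identified as such, and the visible text does not clearly place this study among them.
- Worst-grade laboratory tables: exposed under the visible text.
- Treatment-related AEs, SAEs and select AEs: exposed only through misattribution.
- AEs leading to nivolumab discontinuation: essentially untouched, since a drug started after nivolumab stopped cannot have caused the stop.

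**The case against.** The strongest reply is that no formal endpoint is mechanically affected. The exposed tables are supportive, an all-cause table claims no attribution, and Protocol 10.3 already rules out direct comparison with other countries' data. This stands and limits the weight of the point. A reader might infer that the primary endpoint is biased. The documents do not support that: it counts treatment-related events only, and nothing in them allows misattribution to be quantified.

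A second reply is that the long window is justified. Protocol 6.1 equates 5 months of contraception with 30 days plus about five half-lives, which leaves roughly 5 × 30 − 30 = 120 days. On the protocol's own figures, drug exposure lasts through the 100 days. This also stands. It argues against cutting the window short, and against replacing the laboratory tables with values from before the switch, since that could discard delayed nivolumab effects.

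Third, SAP 7.3.6 gives no frequency or timing. It does not show that switching inside the window is common, and time after the last dose is not time on a new drug.

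Fourth, text is redacted in and after SAP 7.6.8, after SAP 7.4.2.2 and before Protocol 7.7.2, so a rule there cannot be excluded. SAP 6.1.2, where the window is defined, is readable and has none.

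Finally, by-subject listings would let a reader match dates by hand. That is possible with about 100 participants, but it does not correct a summary table.

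**Conclusion.** The point holds for the all-cause AE, SAE and select-AE tables, the IMAE tables and the worst-grade laboratory tables. As far as the visible text shows, they can include toxicity of a treatment started after nivolumab, with nothing to mark it. The direction is upward, and early stoppers are the most exposed.

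The size is unknown. It rests on how many participants switch inside the window, how soon, and how toxic the next treatment is, and the documents give none of these. The per-participant steps of 1.4, 3.3 and 1.0 points are firm; the wider illustration is not an estimate.

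It does not follow that the treatment-related endpoints are biased or that the window is wrong. This is a cheap improvement to how the safety tables can be read.

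**What to change.** Keep the current window and the current tables as the main analysis. In SAP 6.1.2 and 7.6:

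- Define a flag for AEs with onset, and laboratory values collected, on or after the start of subsequent systemic cancer therapy. The dates are already collected for the SAP 7.3.6 listing.
- Show the flag in the by-subject listings.
- Add sensitivity versions of the all-cause AE, SAE, select-AE, IMAE and worst-grade laboratory tables that exclude flagged records, so that both versions are shown for laboratory data too.

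The cost is SAP wording, one derived variable and a few repeated tables, with no new visits or data. The drawback is that the sensitivity version observes switchers for less time and may omit some genuine delayed nivolumab effects. That is why it should stand beside the main tables and not replace them.
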